6.2.3.2 Secondary Endpoints

In order to assess the loss of pain symptoms, “proportion of subjects with a maximum NRS score of 0 during the 28 days before the final dose of study drug” (ie, proportion of subjects with “no pain” during the 28 days before the final dose of study drug) is to be evaluated.

The mean NRS score is designated to assess overall pain symptoms in a single menstrual cycle.

Additionally, the number of days without pain symptoms (NRS = 0) during the 28 days before the final dose of study drug is designated to assess frequency of pain symptoms.

Other commonly used safety endpoints, such as AEs and vital signs, are also included.

6.2.3.3 Additional Endpoints

Furthermore, the proportion of days using analgesics is also assessed since patients who experience pain symptoms usually use analgesics.

For the additional evaluation of the safety and efficacy of TAK-385 and pharmacodynamics of TAK-385 (LH, FSH, E₂, and P concentrations) in subjects with uterine fibroids are also to be evaluated.

6.3 Premature Termination or Suspension of Study or Investigational Site

6.3.1 Criteria for Premature Termination or Suspension of the Study

The study will be completed as planned unless one or more of the following criteria are satisfied that require temporary suspension or early termination of the study.

CONFIDENTIAL

- New information or other evaluation regarding the safety or efficacy of the study medication that indicates a change in the known risk/benefit profile for the compound, such that the risk/benefit is no longer acceptable for subjects participating in the study.
- Significant violation of Good Clinical Practice (GCP) that compromises the ability to achieve the primary study objectives or compromises subject safety.

6.3.2 Criteria for Premature Termination or Suspension of Investigational Sites

A study site may be terminated prematurely or suspended if the site (including the investigator) is found in significant violation of GCP, protocol, or contractual agreement, is unable to ensure adequate performance of the study, or as otherwise permitted by the contractual agreement.

6.3.3 Procedures for Premature Termination or Suspension of the Study or the Participation of Investigational Sites

In the event that the sponsor, an institutional review board (IRB) or regulatory authority elects to terminate or suspend the study or the participation of an investigational site, a study-specific procedure for early termination or suspension will be provided by the sponsor; the procedure will be followed by applicable investigational sites during the course of termination or study suspension.

7.0 SELECTION AND DISCONTINUATION/WITHDRAWAL OF SUBJECTS

All entry criteria, including test results, need to be confirmed prior to randomization.

7.1 Inclusion Criteria

Subject eligibility is determined according to the following criteria prior to entry into the study.

7.1.1 Inclusion Criteria for Entering the Screening (at VISIT 1)

1. In the opinion of the investigator or subinvestigator, the subject is capable of understanding and complying with protocol requirements.
2. The subject signs and dates a written, informed consent form prior to the initiation of any study procedures.
3. Prior to VISIT 1, the subject has a diagnosis of uterine fibroids confirmed by transvaginal ultrasound, abdominal ultrasound, magnetic resonance imaging (MRI), computed tomography (CT), or laparoscopy, and has never received surgical treatment for the myoma (measurable noncalcified myoma with a longest diameter of ≥ 3 cm).
4. The subject is a premenopausal Japanese woman.
5. The subject is aged 20 years or older on the day of signing and dating the informed consent form.
6. The subject has 1 or more measurable noncalcified myomas with a longest diameter of ≥ 3 cm confirmed by transvaginal ultrasound.
7. The subject has experienced 1 or more regular menstrual cycles (25 to 38 days) immediately prior to VISIT 1 and that should include menstrual bleeding of at least 3 consecutive days.
8. The subject who is sexually active with a nonsterilized* male partner agrees to use routinely adequate contraception from signing of informed consent throughout the duration of the study.

*Definitions and acceptable methods of contraception are defined in Section [9.1.9 Contraception and Pregnancy Avoidance Procedure](#) and reporting responsibilities are defined in Section [9.1.10 Pregnancy](#).

7.1.2 Inclusion Criteria for Entering the Run-in (at VISIT 2)

9. The subject has experienced regular menstrual cycles (25 to 38 days) immediately prior to VISIT 2 that should include menstrual bleeding of at least 3 consecutive days (at least 2 regular menstruation cycles to be confirmed by Inclusion criteria #7 and #9).

7.1.3 Inclusion Criteria for Entering the Treatment (at VISIT 3)

10. The subject has 1 or more measurable noncalcified myomas, with a longest diameter of ≥ 3 cm confirmed by transvaginal ultrasound (the same myoma should be measured as in Inclusion criterion #6).
11. The subject has a maximum NRS score of ≥ 4 in 1 menstrual cycle just before VISIT 3.
12. The subject has pain symptoms associated with uterine fibroids of at least 2 days in 1 menstrual cycle just before VISIT 3.
13. The subject has experienced regular menstrual cycles (25 to 38 days) after VISIT 1 that should include menstrual bleeding of at least 3 consecutive days (at least 3 regular menstruation cycles to be confirmed by Inclusion criteria #7, #9 and #13).

7.2 Exclusion Criteria

Any subject who meets any of the following criteria will not qualify for entry into the study.

1. The subject has received any investigational compound within 24 weeks prior to the start of the administration of the study medication for the day of first menstruation after VISIT 1.
2. The subject has received TAK-385 (including placebo) in a previous clinical study.
3. The subject is an immediate family member, study site employee, or is in a dependant relationship with a study site employee who is involved in conduct of this study (eg, spouse, parent, child, sibling) or may consent under duress.
4. The subject has lower abdominal pain due to irritable bowel syndrome or severe interstitial cystitis.
5. The subject has a current history of thyroid gland disorder with irregular menstruation, or has a potential for irregular menstruation due to thyroid gland disorder, as determined by the investigator or subinvestigator.
6. The subject has a previous or current history of pelvic inflammatory disease within the 8 weeks prior to VISIT 1.
7. The subject has a positive Pap smear test result conducted within the 1 year prior to VISIT 1 (if there are no previous test results, those who were judged positive in the test conducted before VISIT 2).

Note: “Positive” is defined as the result that falls in classes other than I or II in the Nichibo Classification or any result other than negative for intraepithelial lesion or malignancy (NILM) in the Bethesda System.

8. The subject has a history of panhysterectomy or bilateral oophorectomy.
9. The subject has had markedly abnormal uterine bleeding or anovulatory bleeding, as determined by the investigator or subinvestigator.

10. The subject has a malignant tumor or a history of a malignant tumor within the 5 years prior to VISIT 1.
11. The subject has been treated with selective estrogen receptor modulators (SERMs) (excluding drugs for external use and dietary supplements) within the 4 weeks prior to VISIT 2.
12. The subject has been treated with any of the following drugs within the 8 weeks prior to VISIT 2: oral contraceptive or sex hormone preparations (norethindrone, norethisterone, medroxyprogesterone, estrogen, or other progestins), and within the 16 weeks prior to VISIT 2: GnRH analogues, dienogest, danazol, or aromatase inhibitors (for 1- and 3-month sustained-release preparations, within the 20 and 28 weeks prior to VISIT 2, respectively).
13. The subject has a previous or current history of severe hypersensitivity or severe allergies to drugs.
14. The subject has nondiagnosable abnormal genital bleeding.
15. Female subject who is pregnant, lactating, or intending to become pregnant or to donate ova prior to signing of informed consent, during the study period, or within 1 month after the end of the study.
16. The subject has clinically significant cardiovascular disease (eg, myocardial infarction or unstable angina pectoris within the 24 weeks prior to VISIT 1) or uncontrollable hypertension (eg, resting systolic blood pressure ≥ 180 mmHg or diastolic blood pressure ≥ 110 mmHg at Screening and Run in).
17. The subject is inappropriate for participation in this study based on standard 12-lead ECG findings, as determined by the investigator or subinvestigator.
18. The subject has active liver disease or jaundice, or with alanine aminotransferase (ALT), aspartate aminotransferase (AST), or bilirubin (total bilirubin) > 1.5 times the upper limit of normal (ULN) in the clinical laboratory tests at VISIT 1 and 2.
19. The subject has previous or current history of diseases considered to be inappropriate for participation in this study, including severe hepatic impairment, jaundice, renal impairment, cardiovascular disease, endocrine system disease, metabolic disorder, pulmonary disease, gastrointestinal disease, neural disease, urological disease, immune disease, or mental disorder (especially depression-like symptoms) or suicide attempt resulting from a mental disorder.
20. The subject has a previous or current history of drug abuse (defined as any illicit drug use) or alcohol abuse.
21. The subject is inappropriate for participation in this study for other reasons, as determined by the investigator or subinvestigator.

7.3 Excluded Medications and Treatments

7.3.1 Excluded Medications

Use of the following drugs is prohibited in this study.

7.3.1.1 *Sex Hormone and Anti-hormone Preparations*

Use of the following drugs is prohibited from VISIT 1 to 7 (or until early termination) to avoid confounding of the assessment of safety, efficacy and pharmacodynamics.

- Danazol
- GnRH analogues
- Dienogest
- Oral contraceptives and other sex hormone preparations (norethindrone, norethisterone, medroxyprogesterone, estrogen, and other progestins)
- Aromatase inhibitors
- Herbal medicines with indications related to menstruation (eg, Tokishakuyakusan and Keishi-bukuryogan)

7.3.1.2 *Other Drugs That May Affect Efficacy, Safety, or Pharmacokinetic Assessment of TAK-385*

Use of the following drugs (excluding drugs for external use and dietary supplements) is prohibited from VISIT 1 to 6 (or until early termination).

- Steroid hormones
- Anti-epileptic drugs
- Anti-convulsants
- Anti-depressants
- Anti-psychotics (major tranquilizers)
- Ergot alkaloids
- St. John's wort (*Hypericum perforatum*)
- P-glycoprotein (P-gp) inhibitors
- P-gp inducers
- Cytochrome P450 inducers
- SERMs
- Analgesics (excludes those specified in Section 7.3.2; use of external preparations for the treatment of pain not associated with uterine fibroids is permitted)

CONFIDENTIAL

7.3.2 Drugs Permitted with Condition

Use of analgesics is **ONLY permitted under the following conditions** from VISIT 1 to 6 (or until early termination). This restriction was set because it is likely to have an impact on the evaluation of primary, secondary and additional endpoints. Analgesics refer to drugs containing compounds that have indications for pain symptoms in the package inserts and antispasmodic drugs which possess indications for gynecological or urological disease in the package inserts.

- For severe pain **associated with uterine fibroids**; Loxoprofen can be used as the first choice medicine. If loxoprofen cannot be used for various reasons, other non-steroidal anti-inflammatory drugs (NSAIDs) can be used.
- For treatment of AE, etc. **NOT associated with uterine fibroids** (eg, common cold); Acetaminophen can be used as the first choice medicine. If acetaminophen cannot be used for various reasons, other NSAIDs can be used. In addition to acetaminophen and NSAIDs, analgesics for external use are also permitted to be used.

Analgesics for pain associated with uterine fibroids will be provided by the site in accordance with the approved package labeling.

The investigator or subinvestigator should instruct subjects to take analgesics as directed and to avoid using them under a fasted state. The investigator or subinvestigator should instruct subjects not to casually use analgesics for prophylactic purposes. The investigator or subinvestigator should also instruct subjects to record their maximum pain symptoms during the past 24 hours, considering pain symptoms before taking analgesics, in the patient diary (NRS). Subjects must record the use of analgesics to relieve pain from uterine fibroids every day in the patient diary.

In addition, analgesics can be used in the cases as follows.

- When the reason for use is other than AE, concurrent condition or target disease (eg, scopolamine butylbromide for MRI preparation)
- Codeine which is not intended to relieve pain associated with uterine fibroids (eg, codeine phosphate in a combination cold remedy)

7.3.3 Excluded Treatments

Surgical treatment of uterine fibroids, and use of intrauterine device (IUD) are prohibited from VISIT 1 to VISIT 7 (or until early termination).

7.4 Diet, Fluid and Activity Control

The investigator, subinvestigator, and study collaborator should advise subjects to comply with the following instructions:

1. Make the scheduled visits on time, and undergo examinations and tests as requested. If the subject cannot make a scheduled visit, she should inform the study site as soon as possible.
2. Report the subjective symptom and objective symptom at each visit, including its contents, the date of occurrence, intensity, outcome, and date of outcome.

CONFIDENTIAL

3. If any abnormality has occurred between visits, such as worsening of a bleeding symptom, the subject should immediately report to the investigator, subinvestigator, or study collaborator by telephone or other means, and ask for instructions.
4. If the subject visits another medical institution during the study period, she should inform the investigator or subinvestigator about the reasons for the visit and treatment received.
5. If the subject takes any drugs other than those prescribed by the investigator or subinvestigator (including over-the-counter medications), she should report this at the next visit.
6. The subject should record in the patient diary every day (keeping a daily record of pain symptoms and entering information on the use of study drugs and analgesics are very important for the evaluation of TAK-385 in this study).
7. The subjects are instructed to use adequate contraception during the study period.
8. The subjects will be asked to avoid excessive exercise and activities, and maintain a normal daily routine during the study period. In particular, subjects must avoid drinking and eating excessively on the day before each visit, and should also avoid drinking grapefruit juice to any extent possible during the study period.
9. The subject should bring all unused study drugs, empty blister card(s) of study drug, and the patient diary to each visit.
10. The subject should start taking the study drug on the day of first menstruation after VISIT 1, and start taking the study drug for the Treatment from the day of VISIT 3. The subject should take the study drug every day as instructed by the investigator or subinvestigator. Taking the study drug every day is very important for the drug to show its expected effects.
11. The subject should take study drugs every day before breakfast during the Run-in and the Treatment, and should try to take the study drug at approximately the same time each day. If the subject forgets to take the study drug before breakfast, she should take it before lunch on the same day. If the subject forgets to take the study drug in both cases (ie, before breakfast and before lunch), she should take it before dinner on the same day. The subject should avoid carrying over the missed dose to other day and taking multiple doses together on the same day. The date of administration and whether the drug was taken before a meal should be properly recorded in the patient diary.

For the scheduled study site visit from VISIT 2 through 6, follow the instructions below:
<VISIT 2, 3 and 6>

On the days of the scheduled study site visit, the subject should try to visit the study site without taking the TAK-385 tablet in the morning and undergo the designated study procedures as far as possible. Even if the subject cannot visit the study site in the morning, she should still come to the study site without taking the TAK-385 tablet.

<VISIT 4 and 5>

On the days of the scheduled study site visit, the subject should try to visit the study site without taking the TAK-385 tablet in the morning and undergo the designated study procedures as far as possible. If the subject cannot visit the study site in the morning, she must take the TAK-385 tablet before breakfast, and report to the investigator or subinvestigator that she has taken the drug.

12. When the subject needs to take analgesic drugs due to severe pain associated with uterine fibroids, the subject should comply with the investigator's or subinvestigator's instructions before taking the analgesic drug, and try to avoid taking it in a fasted state as far as possible. The subject should also not take the analgesic drug casually or for prophylactic purposes. In cases where the subject has to take an analgesic drug, she is required to properly record her pain symptoms which occur before taking analgesics in the patient diary (NRS) and to record analgesic use in the patient diary.
13. The subject may use acetaminophen as the first choice medicine in certain circumstances, such as occurrence of an AE, that requires an analgesic for purposes other than to relieve pain from uterine fibroids. In this case, avoid casually using it for prophylactic purposes.

7.5 Criteria for Discontinuation or Withdrawal of a Subject

The primary reason for discontinuation or withdrawal of the subject from the study or study medication should be recorded in the electronic case report form (eCRF) using the following categories. For subject failure, refer to Section [9.1.14](#).

1. Death. The subject died on study and caused early termination of study treatment.

Note: If the subject dies on study, the event will be considered as serious adverse event (SAE). Refer to Section [10.2.2](#) for the reporting procedures.

2. Adverse event (AE). The subject has experienced an AE that requires early termination because continued participation imposes an unacceptable risk to the subject's health or the subject is unwilling to continue because of the AE.

- Liver Function Test (LFT) Abnormalities

Study medication should be discontinued immediately with appropriate clinical follow-up (including repeat laboratory tests, until a subject's laboratory profile has returned to normal/baseline status, see Section [9.1.8](#)), if the following circumstances occur at any time during study medication treatment:

- ALT or AST $>8 \times \text{ULN}$, or
- ALT or AST $>5 \times \text{ULN}$ and persists for more than 2 weeks, or
- ALT or AST $>3 \times \text{ULN}$ in conjunction with elevated total bilirubin $>2 \times \text{ULN}$ or international normalized ratio (INR) >1.5 , or
- ALT or AST $>3 \times \text{ULN}$ with appearance of fatigue, nausea, vomiting, right upper quadrant pain or tenderness, fever, rash and/or eosinophilia ($>5\%$).

- Hypoestrogenic symptoms

The investigator or subinvestigator makes an overall risk-benefit assessment for the subject when any of the following events that can be considered related to the pharmacological effect of TAK-385 occur, and decides whether to stop the drug administration based on the intensity and frequency of the event:

- Hot flush, feeling hot, flushed face, shoulder stiffness, headache, insomnia, dizziness, perspiration, menopausal depression, decreased libido, feeling cold, visual disturbance, emotional lability.

- ECG abnormality

The subject judged by the investigator or subinvestigator to be inappropriate for continuation of the study based on standard 12-lead ECG findings.

3. Protocol deviation. The discovery after randomization that the subject failed to meet protocol entry criteria or did not adhere to protocol requirements, and continued participation poses an unacceptable risk to the subject's health.
4. Lost to follow-up. The subject did not return to the clinic and attempts to contact the subject were unsuccessful. Attempts to contact the subject must be documented.
5. Withdrawal by subject. The subject wishes to withdraw from the study. The reason for withdrawal, if provided, should be recorded in the eCRF.

Note: All attempts should be made to determine the underlying reason for the withdrawal and, where possible, the primary underlying reason should be recorded (withdrawal due to an AE or lack of efficacy should not be recorded in the "Withdrawal by subject" category).

6. Study terminated by sponsor. The sponsor terminates the study.
7. Pregnancy. The subject is found to be pregnant.

Note: If the subject is found to be pregnant, the subject must be withdrawn immediately. The procedure is described in Section [9.1.10](#).

8. Lack of efficacy. The investigator or subinvestigator judges TAK-385 shows no efficacy based on the menstrual blood loss, menstrual status, and use of analgesics (eg, a notable increase in the frequency of taking analgesics due to intolerable pain after start of study drug administration) and judges continued participation in the study would pose an unacceptable risk to the subject.
9. Other.

Note: The specific reasons should be recorded in the "specify" field of the eCRF.

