TAK-385 has been synthesized at Takeda Pharmaceutical Company Limited (TPC) and is an orally active, nonpeptide, GnRH antagonist with a novel structure. TAK-385 antagonizes GnRH on the GnRH receptors that are present in the pituitary anterior lobe basophiles (secretory cells), and inhibits the GnRH-stimulated secretion of luteinizing hormone (LH) and follicle-stimulating hormone (FSH) from these cells. As a result, the drug decreases blood concentrations of hormones, including estradiol (E₂) and progesterone (P), and induces amenorrhea. Therefore, TAK-385 is expected to improve the clinical symptoms observed in patients with uterine fibroids. As TAK-385 is a GnRH antagonist, it causes no flare up and has a faster onset of action than GnRH agonists. Unlike GnRH agonists, which are given either subcutaneously (SC) or intranasally, TAK-385 is a nonpeptide preparation and can be administered orally.

For the above reasons, the development of TAK-385 for the treatment of benign sex hormone-dependent gynecological diseases, such as endometriosis and uterine fibroids, has been progressing in Japan and overseas.

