5.0 STUDY OBJECTIVES AND ENDPOINTS

5.1 Objectives

5.1.1 Primary Objective

The primary objective of this study is to evaluate the efficacy of TAK-385 40 mg administered orally once daily for 12 weeks, compared with placebo in subjects having pain symptoms associated with uterine fibroids.

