9.1.17 Pain Symptoms, Other Clinical Symptoms, and QOL

Pain symptoms are evaluated using the NRS score. The investigator or subinvestigator distributes the patient diary to consented subjects. Subjects fill out the patient diary every day from VISIT 1 to the day before VISIT 6 (or until early termination). Subjects record pain symptoms within 24 hours associated with uterine fibroids (NRS score), menstruation, and use of analgesics. If subjects use any analgesics for pain associated with uterine fibroids, they should record this fact in the patient diary along with the accompanying pain symptoms before use of analgesics. The start/end date of menstruation must be recorded in CRF in reference to the patient diary by the investigator or subinvestigator. If there is anything unclear or insufficient description in the patient diary, queries may be made to the subject, and corrections to the patient diary are recorded by the subject in a change history that captures the old information, the new information, identification of the person making the correction and the date of the correction. If it is impossible to make queries to the subject at site visits, queries will be made to the subject with telephone calls or other means, and corrections to the patient diary are recorded by the investigator or subinvestigator in a change history that captures the old information, the new information, identification of the person making the correction and the date of the correction.

The uterine fibroid symptom and QOL (UFS-QOL) score is used to evaluate other clinical symptoms and the QOL of subjects. The investigator or subinvestigator distributes the UFS-QOL questionnaire at VISITS 3 and 6, and has subjects fill it out before physical examination at site visit.

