7.1.1 Study Definitions

Duration of exposure to double-blind study drug (days):

Date of last dose of double-blind study drug - date of first dose of double-blind study drug +
1

Double-blind study drug compliance (%):

Number of double-blind study drugs taken/duration of exposure to double-blind study drug*
100 (rounded to 1 decimal places)

Disease Duration (years):

((year of informed consent*12 + month of informed consent) -(year of first defined diagnosis of uterine fibroids*12 + month of first defined diagnosis of uterine fibroids))/12 (rounded to 1 decimal places)

Maximum Drug Holidays (days):

Maximum number of consecutive days on which the subject does not take the study drug for the treatment period

Proportion of subjects with a maximum NRS score of 1 or less during the 28 days before the final dose of study drug

CONFIDENTIAL

((number of subjects with a maximum NRS score of 1 or less during the last 28 days of the treatment)/(number of subjects with available data during the 27 days before the final dose of study drug and the date))*100 (rounded to 1 decimal places)

Similarly, for proportion of subjects with a maximum NRS score of 0 during the 27 days before the final dose of study drug and the date, its numerator will be defined as number of subjects with a maximum NRS score of 0 during the 27 days before the final dose of study drug and the date.

Number of days without pain symptoms (NRS = 0) during the 28 days before the final dose of study drug (%):

((number of days without pain symptoms (NRS = 0) during the last 28 days of the treatment)/(number of days with available data during the last 28 days of the treatment))*100 (rounded to 1 decimal places)

Maximum NRS score at baseline

Maximum NRS score from first day of menstrual period confirmed at Visit 2 to a day prior to menstrual period confirmed at Visit 3

Mean NRS score at baseline

Mean NRS score from first day of menstrual period confirmed at Visit 2 to a day prior to menstrual period confirmed at Visit 3

Maximum NRS score from Day 1 to 28, 29 to 56, and 57 to 84

Maximum NRS score from Day 1 to earlier of Day 28 or Follow-up Day 3.

Similarly, Maximum NRS score from Day 29 to 56 and from Day 57 to 84 will be defined as maximum NRS score from Day 29 to earlier of Day 56 or Follow-up Day 3 and from Day 57 to earlier of Day 84 or Follow-up Day 3, respectively.

Mean NRS score from Day 1 to 28, 29 to 56, and 57 to 84

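### No planned analysis counts subjects who stop treatment early as failures, so an early stopper can be a responder for a 12-week objective; lack-of-efficacy item 8 also needs reconciling with the pain data

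*Protocol*

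**What the plan says.** **Objective and endpoint.** Protocol 5.1.1 asks about 12 weeks of once-daily TAK-385 40 mg, "compared with placebo in subjects having pain symptoms associated with uterine fibroids". The primary endpoint (Protocol 5.2.1 and 13.1.3) is the proportion with a maximum NRS of 1 or less in the 28 days tied to the final dose. SAP 7.1.1 defines the numerator as the "number of subjects with a maximum NRS score of 1 or less during the last 28 days of the treatment". Its denominator is subjects with available data on the final-dose date and the 27 days before it.

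**Who is analysed and with what data.** Protocol 13.1.1 puts every randomized subject with at least one dose in the FAS. SAP 7.1.4 imputes nothing unless otherwise specified. Protocol 9.1.17 ends the diary at the day before VISIT 6 or at early termination.

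**Other planned views.** SAP 7.8.1.2 repeats the primary analysis in the PPS. SAP 7.8.2.2 reports the same proportion for Days 1-28, 29-56 and 57-84. SAP 7.3.5 tabulates completion and reasons for discontinuation by arm, and SAP 7.7 tabulates exposure.

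**Lack of efficacy.** Protocol 7.5 item 8 reads: "The investigator or subinvestigator judges TAK-385 shows no efficacy based on the menstrual blood loss, menstrual status, and use of analgesics". The example given is "a notable increase in the frequency of taking analgesics due to intolerable pain after start of study drug administration". The item also requires that the investigator "and judges continued participation in the study would pose an unacceptable risk to the subject". On the data side, Protocol 9.1.17 says: "Subjects record pain symptoms within 24 hours associated with uterine fibroids (NRS score), menstruation, and use of analgesics".

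**The concern.** The scoring window moves with the last dose. A completer is scored on the third treatment month. A subject who stops early, for hypoestrogenic symptoms or any other reason, is scored on an earlier stretch. If that stretch was nearly pain-free she is a success, even though she did not take the 12 weeks of treatment that the objective describes. If stopping differs between arms in number, timing or reason, the primary comparison mixes effect on pain with ability to stay on treatment, and no planned table separates the two.

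Item 8 feeds one kind of early stop. Two of its three named signs concern bleeding, and the measure that defines the primary endpoint is not named.

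**Working it through.** **1. The plan's own figure.** Inputs from Protocol 13.3: 20% against 65%, two-sided 5%, Fisher's exact test. Full enumeration of both binomials gives power 90.4% at 28 per group, so the stated figure of more than 90% reproduces. At 32 per group it is 95.1%.

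**2. Where the window falls.** Window = (last dose − 27) to last dose.

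| Last dose | Days scored |
|---|---|
| Day 84 | 57 to 84 |
| Day 70 | 43 to 70 |
| Day 40 | 13 to 40 |
| Day 35 | 8 to 35 |

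**3. Does another analysis catch this?** The PPS analysis uses the same variable. The Day 57-84 summary ends at the earlier of Day 84 or Follow-up Day 3, that is, last dose + 3 days. A last dose before Day 54 leaves no day in it (53 + 3 = 56). A last dose on Days 54-56 leaves at most one to three days, if a diary was still kept. Under SAP 7.1 the denominator is subjects with non-missing responses, so those without data leave the table instead of counting as failures. A subject who stops on Day 60 is scored on Days 57-63 at most and can still be a responder.

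**4. Size.** One subject is 1/32 = 3.1 points. The number of early stops is unknown, so k below is an assumption. Taking all 32 per arm as treated, and stoppers as otherwise like the rest of their arm, scoring k of them as non-responders gives a rate of p × (1 − k/32). With k = 4 on TAK-385: 0.65 × 28/32 = 56.9%, a fall of 8.1 points.

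| k | Power, k stops in each arm | Power, k stops on TAK-385 only |
|---|---|---|
| 0 | 95.1% | 95.1% |
| 2 | 92.2% | 90.2% |
| 4 | 88.4% | 82.7% |
| 6 | 83.9% | 72.6% |

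**5. What non-responder scoring can do wrong.** Suppose pain response is truly 40% in both arms and k of 32 placebo subjects are stopped for bleeding regardless of pain. The scored placebo rate is 0.40 × (1 − k/32): 35% for k = 4 and 30% for k = 8. Two-sided error rises from 3.0% (k = 0) to 4.3% and 8.9%, nearly all of it in favour of the drug.

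**6. Can an untreated subject's window miss menstruation?** Assumptions: VISIT 3 uniform on menses days 1-5, cycles of 25-38 days, five bleeding days, no drug effect, window cut at Day 1. Three cycle models were simulated with 200,000 subjects each: every cycle drawn afresh; length fixed within subject; subject mean 27-36 days with SD 2.

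| Last dose | Share with no bleeding day in the window |
|---|---|
| Up to Day 28 | 0% |
| Day 33 (peak) | about 21-29% |
| Days 40-50 | 0% |
| Day 70 | about 8-19% |
| Day 84 | 0-2% |
| Average over Days 7-83 | about 3-4% |

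**7. Item 8 beside the data collected.** The diary holds NRS, menstruation and analgesic use. No procedure in Protocol 9.1 or 9.3 measures the amount of blood lost; the PBAC appears only in accounts of the Phase 2 study. Item 8 thus names one quantity that is not measured and leaves out the daily pain score that is.

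**The case against.** The final-dose window is deliberate: the Phase 2 rates behind the sample size use the same definition. Fixed-window results, reasons for discontinuation and exposure are already planned by arm. The rules for analysis sets and acceptable data sit in the Handling Rules for Analysis Data, which are not among these documents and may deal with early stoppers. All of this stands, and it is why the primary analysis need not change. It does not fill the gap: the planned tables do not link a subject's stopping day and reason to her responder status, and none counts her as a failure.

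Three stronger readings are tempting, and the documents do not support them.

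- *Item 8 rests on bleeding alone.* It also names analgesic use, with intolerable pain as its example, and requires a judgement of unacceptable risk. Protocol 6.2.1 itself links pain to bleeding, so bleeding is not foreign to the question.
- *A subject who bleeds is recognisably on placebo.* Protocol 4.1 says the drug lowers sex hormones "and induces amenorrhea", so menstrual status carries some information. But no amenorrhea rate is given, and Protocol 4.2 lists metrorrhagia, genital hemorrhage and irregular menstruation among the common Phase 2 events, with metrorrhagia and irregular menstruation rising with TAK-385 dose. Menstruation is in the diary whatever item 8 says.
- *Placebo stoppers often become responders because no menstruation fell in their window.* The average share is only about 3-4%, and a subject stopped for bleeding has normally just bled. A window without bleeding is also not a response: every recorded NRS must be 1 or less, and Protocol 6.2.1 says pain occurs outside menstruation too. Such an error would in any case work against the drug.

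**Conclusion.** The scoring gap is real, and closing it is a cheap improvement rather than a repair of the primary analysis. As written, an early stopper can count as a responder on an earlier treatment month, and no planned analysis in these documents treats her as a failure. Each such subject is worth 3.1 points in her arm. The total depends on the number, timing and arm of early stops, which the documents do not give; the figures for k stops are illustrations. The conclusion also assumes that the unseen handling rules do not already settle the matter.

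The item 8 point is narrower: a mismatch between the signs it names, the pain objective and the data collected. The documents do not show that it unblinds the trial or biases the result.

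**What to change.** **SAP 7.8.1.2.** Keep the primary analysis. Add a supplementary Fisher's exact test in the FAS with all treated subjects in the denominator. A responder must have completed double-blind study drug (the category in SAP 7.3.5) and have a maximum NRS of 1 or less over Days 57-84. Everyone who discontinued early is a non-responder, including those who stop between Day 57 and Day 84.

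**Listing beside it.** For each early stopper, by arm: last-dose day, reason for stopping, and responder status under the primary definition.

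**Protocol 7.5 item 8.** The sponsor should reconcile its wording with the pain objective and with the data collected under 9.1.17. The clinical basis is the sponsor's decision; none is proposed here.

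**Cost.** One extra test, one short listing and a small wording amendment, with no new data collection. The supplementary TAK-385 rate may be slightly lower. If placebo subjects are stopped for bleeding rather than pain, the scoring favours the drug (two-sided error 3.0% rising to 4.3% with 4 stops and 8.9% with 8, at a common 40% response). The analysis should therefore not be reported without the listing.
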